1.3 SUMMARY OF CLINICAL STUDIES

To date, thirteen open label clinical studies (plus three extensions) and 4 single blinded clinical studies utilizing Sci-B-VacTM (also distributed under the trade names Bio-Hep B and Hepimmune) have been completed¹⁶⁻²⁸.

The clinical development of Sci-B-VacTM included: two phase I studies in adults ^{16,17}, three phase II dose-range studies in adults ¹⁶⁻¹⁸ one in children ¹⁹ and four in neonates ²⁰⁻²³, two phase II and one phase III comparative studies in adults ²⁴⁻²⁶, one Phase II study in children²⁷ and one Phase II study in neonates²⁸. Three of the studies (one in adults and two in children) were extended in order to increase the size of the group vaccinated with Sci-B-VacTM. In the adult phase I studies, subjects received 10 µg of Sci-B-VacTM. Sci-B-VacTM was given once to prime the immune memory; the first dose was followed by two booster doses at 1 and 6 months after primary immunization¹⁶. This immunization schedule is set by convention. In the first adult Phase II study in Singapore¹⁶, subjects were randomized to receive 5 µg or 10 µg of Sci-B-VacTM in three injections. Once tolerability/safety and dose-dependent efficacy were demonstrated, the clinical development of two more adult dose-range studies were performed in Thailand and Israel ^{17,18}, followed by a dose-range study performed in Poland with children¹⁹ and four neonate studies in Poland, Singapore and Vietnam²⁰⁻²³. After seroconversion rates and the efficacy/dose relationship were more firmly established, five comparative studies which assessed the efficacy of Sci-B-VacTM relative to that of conventional yeast derived vaccines were performed in adults, children and neonates²⁴⁻²⁸.

From the early phase II studies it became evident that a significant number of vaccinees develop high anti-HBs titers following vaccination. In study HBN014-01²³, conducted in Vietnam, a dose-response relationship could be demonstrated. More vaccinees who received the 5 µg dose/injection had anti-HBs titers ranging from 1001-10,000 mIU/ml as compared to those who received the 2.5 µg dose/injection. More than 60% of the vaccinees in the 5 µg dose group developed these high titers within three months after the third vaccination. At the end of the study 95.6% (196/205) of the subjects were seroprotected.

The high efficacy of Sci-B-VacTM was further confirmed in adults^{25,26} and in neonates²⁸. In these comparative controlled studies conducted in Israel, more than 50% of adult vaccinees who received the 10 µg/dose and neonates who received the 2.5 µg dose had anti-HBs titers above 10,000 mIU/ml after the third vaccination. These percentages were greater than those observed in vaccinees who received the yeast-derived vaccines. Furthermore, no non-responders were observed in

	Protocol No.: SciB018
	Version and Date: Version 2.0, September 9, 2015 Amendment 1

immunized neonates who received 2.5 µg Sci-B-Vac™. In adults, the number of non-responders who received Sci-B-Vac™ was very small (3.5%, 18/513) as compared to vaccinees immunized with Engerix-B® (13.7%, 43/415).

1.4 STUDY RATIONALE

Each Sci-B-Vac™ lot released to the market is tested in comparison to a reference batch, which has to be tested in a human clinical trial. Therefore, SciVac Ltd. is conducting this study to evaluate the efficacy of a Sci-B-Vac™ batch in support of its qualification as new reference standard. In accordance with the European Pharmacopeia (Ph.Eur. 1056), this reference standard is to elicitated at least 95% seroprotection in young, healthy subjects.

2 STUDY OBJECTIVES

2.1 PRIMARY OBJECTIVE

To validate the new in-house reference standard vaccine for routine quality control purposes, in compliance with the European Pharmacopeia and the Israeli Ministry of Health.

2.2 SECONDARY OBJECTIVES

1. To characterize the immunological response throughout the study.
2. To monitor the subjects for safety throughout the study period

2.3 EXPLORATORY OBJECTIVES

1. To collect blood samples for the *in vitro* validation of anti-HBs, anti-preS1 and anti-preS2 antibodies assays.
2. To assess the anti-preS1 and anti-preS2 antibodies responses upon vaccination.
3. To investigate additional protective mechanisms of action and the type of immune response triggered by the vaccination. No genetic tests will be performed.

3 STUDY ENDPOINTS

3.1 PRIMARY ENDPOINT

Seroprotection rate (SPR), defined as the proportion of subjects with anti-HBs antibody titer at least equal to 10mIU/ml, at Month 7 (i.e. one month after the third immunization with Sci-B-Vac™). Subjects early terminated from the study for any reason at any time while having an anti-HBs antibody concentrations $\geq 10\text{mIU/ml}$ will be considered among those who met endpoint.

3.2 SECONDARY ENDPOINTS

1. SPR one month after the first injection and at every month until Month 6 inclusive and at months 9 and 12.
2. Percentage of subjects with anti-HBs antibodies titer $\geq 100\text{mIU/ml}$ at Month 0, and then at every month until Month 7 inclusive and at months 9 and 12.

	Protocol No.: SciB018
	Version and Date: Version 2.0, September 9, 2015 Amendment 1

- The geometric mean concentration (GMC) as determined by anti-HBsAg antibody titers at Month 0, then at every month until Month 7 inclusive and at months 9 and 12.

3.3 EXPLORATORY ENDPOINTS

- The anti-preS1 antibody titers measured at Month 0, then at every month until Month 7 inclusive and at months 9 and 12.
- The anti-preS2 antibody titers measured at Month 0, then at every month until Month 7 inclusive and at months 9 and 12.

4 STUDY DESIGN

4.1 OVERALL STUDY DESIGN

This will be a post-marketing, open-label, single arm study in healthy volunteers who had never been vaccinated with any hepatitis B vaccine and who are HBs antigen, anti-HBc and anti-HBsAg antibodies seronegative.

The study assessments will be performed as described in the study flow chart (See Appendix A).

This study will consist of three periods:

Screening Period (Visit 1: up to 1 month prior to first vaccination)

After signing of the informed consent form (ICF), screening procedures will be carried out as specified in Section 6.1.1 and Appendix A.

Treatment and Follow-up Period (Visits 2-8: Months 0-6)

Subject identification number will be assigned to all eligible subjects following assessment of inclusion and exclusion criteria.

All eligible subjects will receive Sci-B-Vac™ vaccine. The treatment phase will include three I.M. doses of Sci-B-Vac™ administered in the deltoid muscle on Month 0, Month 1, and Month 6. Subjects will be followed up for safety evaluations and for efficacy (by anti-HBs, anti-pre-S1 and anti-pre-S2 testing), every month. The previous injection site will be inspected before the second and third administration.

The following assessments will be performed during each treatment visit: recording of AEs and concomitant medications, vital signs and blood tests for quantitative anti-HBs, anti-preS1 and anti-preS2 antibodies and safety assessment (including blood and urine laboratory tests). Female subjects will also undergo a urine pregnancy before each injection. Vital signs are not required on follow-up visits when vaccine is not administered.

Post-Vaccination Follow-up Period (Visits 9-11: Months 7, 9 and 12)

Additional subject follow-up visits will take place 1, 3 and 6 months after the last vaccine administration. On each visit, subjects will be inquired about AEs and concomitant medications, and blood samples for quantitative anti-HBs, anti-preS1 and anti-preS2 antibodies levels will be drawn. The last visit (Month 12) is a study termination visit in which all subjects will also undergo physical examination, laboratory safety assessments (CBC, blood chemistry and urinalysis), vital

	Protocol No.: SciB018
	Version and Date: Version 2.0, September 9, 2015 Amendment 1

signs measurement and a 12-lead ECG. In addition, female subjects will undergo a urine pregnancy test.

5 SELECTION OF STUDY POPULATION

5.1 NUMBER OF SUBJECTS

Up to eighty four (84) healthy subjects will be enrolled in the study

5.2 INCLUSION CRITERIA

1. Healthy males and females between 20 and 40 (inclusive) years of age.
2. Subjects who provide written informed consent to participate in the study.
3. Subjects in general good health in the opinion of the investigator as determined by medical history, vital signs and a physical examination.
4. No clinically significant abnormalities in hematology, blood chemistry, or urinalysis lab tests at screening.
5. Women of child-bearing potential must practice an acceptable method of birth control (as specified in Section 8.2) or practice abstinence during the study period or be surgically sterilized, from screening visit throughout the treatment phase and for 28 days after the last injection and agree to undergo repeated pregnancy tests.
6. Subjects must be able to understand the requirements of the study and must be willing to comply with the requirements of the study.

5.3 EXCLUSION CRITERIA

1. Known history of significant medical disorder, which in the investigator's judgment contraindicates administration of the vaccine or may interfere with the subject's compliance or the interpretation of study assessment parameters.
2. Any clinically significant abnormality upon physical examination or in the clinical laboratory tests at screening visit.
3. Treatment with immune suppressive agents.
4. Chronic administration (defined as more than 14 days) of immunosuppressants or other immune-modifying drugs within six months prior to the first vaccine dose.
5. History of HBV infection or confirmed exposure to hepatitis B virus.
6. Previous vaccination against Hepatitis B.
7. Positive for HBsAg, anti-HBsAg antibodies, anti-HBc antibodies, anti-HCV antibodies or anti- HIV antibodies.
8. Drug abusers
9. Known hypersensitivity or allergy to any component of the study vaccine.
10. BMI < 18.5 or ≥ 30 Kg/m².
11. Known concomitant disease or any other medical condition that is considered by the investigator likely to interfere with the subject's compliance or the interpretation of study assessments.

	Protocol No.: SciB018
	Version and Date: Version 2.0, September 9, 2015 Amendment 1

12. Any acute illness (e.g. acute infection) within 48 hours prior to the first study drug administration that is considered of significance by the Principal Investigator.
13. Female subjects: pregnant, lactating or planning a pregnancy.
14. Any confirmed or suspected immunosuppressive or immunodeficient condition.
15. Receipt of blood or immunoglobulin transfusion six months prior to the first vaccine dose and during the course of the trial.
16. Unwilling or unable (in the judgment of the investigator) to comply with all the requirements of the protocol.
17. Participate in another clinical trial within 3 months prior to first vaccination (calculated from the previous study's last dosing date).

5.4 SUBJECT IDENTIFICATION

Each subject who signed the informed consent will be identified by a unique CRC internal identification number and a screening number that will be a unique identifier of the subject through the study. The screening number will include the letter "S", the site number and a sequential chronological order per site of three digits.

Subjects who are dosed will be assigned a recruitment number which will include the letter "R", the site number and a sequential chronological order per site of three digits.

5.5 SCREENING FAILURES

Subjects who fail to meet the entrance criteria at any stage during the screening period are defined as screen failures. All screen failures will be documented on the screening log, which documents the screening number, subject's initials and reason(s) for screen failure. The screening log will be kept in the Investigators Site File.

Screen failure subjects will be withdrawn from the study and will not count towards the total enrolled or total eligible subjects.

5.6 REMOVAL, REPLACEMENT, OR EARLY WITHDRAWAL OF SUBJECTS FROM TREATMENT OR ASSESSMENT

Subjects are free to discontinue their participation in the study at any time and without prejudice to further treatment. The Investigator must withdraw any subject from the study if that subject requests to be withdrawn, or if the subject present positive serological marker of hepatitis B infection, or it is determined that continuing in the study would result in a significant safety risk to the subject.

Subjects discontinued or withdrawn from the study will **not** be replaced after first dosing. If insufficient number of subjects are expected to complete the study, recruitment of additional volunteers will be considered. Approval by the IRB will be required.

The subject's participation in this study may be discontinued due to the following reasons:

- Positive serological marker for hepatitis B infection
- Request of regulatory agency, or Sponsor or Principal Investigator
- Subject withdrew consent
- Adverse event (AE)
- Subject is unwilling or unable to continue the study or is lost-to-follow-up

	Protocol No.: SciB018
	Version and Date: Version 2.0, September 9, 2015 Amendment 1

- Subject is non-compliant with study procedures/study protocol
- Investigator decides that withdrawal from the study is in the best interest of the subject
- Subject needs medication not allowed in the protocol
- Any clinically significant change in subject's medical condition.

5.7 HANDLING OF WITHDRAWALS

If a subject is withdrawn from the study or fails to return either at his/her request or at the Investigator's discretion, every effort should be made to determine the reason. This information will be recorded on the subject's case report form (CRF). All subjects who withdraw from the study prematurely, regardless of cause, should undergo all study termination assessments (see Section 6.1.11). It is crucial to obtain follow-up data for any subject withdrawn because of an AE or abnormal laboratory test finding. In any case, every effort must be made to undertake safety follow-up procedures.

If withdrawal is caused by a Suspected Unexpected Serious Adverse Reaction (SUSAR), it will be reported to the institutional review board/independent ethics committee (IRB/IEC) and Sponsor.

5.8 TERMINATION OF STUDY BY SPONSOR

The Sponsor reserves the right to discontinue the study at any time for any reason. Such reasons may be any of, but not limited to, the following:

- Occurrence of AEs unknown to date in respect of their nature, severity, and duration or the unexpected incidence of known AEs
- Medical or ethical reasons affecting the continued performance of the study

Regulatory Authorities also have the right to terminate the study for any reason.

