10 STATISTICAL METHODOLOGY

A total of 84 subjects, are expected to be recruited into study. The trial will follow-up eligible subject for a total duration of 12 months. One interim analysis is planned to be conducted at the time when approximately 50% of the subjects will reach Month 7 or early terminated the study.

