10.1 INTERIM AND FINAL ANALYSES

One interim analysis is planned for possible early termination of the study.. The interim analysis will be performed at the time when approximately 50% of the subjects will reach Month 7 (1 month after the 3rd vaccine) or early terminated the study..

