10.2 SIGNIFICANCE LEVEL

The overall significance level for this study will be 5% using two-tailed tests.

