2.4 Study Populations

Up to ninety two (92) healthy subjects will be enrolled in the study

Intent-to-Treat (ITT) Population includes all enrolled subjects who were vaccinated at least once with Sci-B-Vac™. The Safety population will be same as ITT population.

Modified Intent-to-Treat (mITT) population is a subset of the ITT set. This set will consist of all enrolled subjects who were vaccinated at least once with Sci-B-Vac™ and had at least one post vaccination follow-up visit, fully comply with the study protocol, had no violation of any of the inclusion/exclusion criteria and did not demonstrate an anamnestic response after the 1st administration of Sci-B-Vac. An anamnestic response revealed by Sci-B-Vac is defined as anti-HBs level above 6000mIU/ml (the highest titer recorded upon Sci-B-Vac 1st injection) in a subject with no detectable anti-HBs antibody at visits 1 and 2. Subjects who early terminated the study but reached the primary endpoint will be included as well. Subjects who did not complete the full-course of vaccination (i.e. 3 injections) and did not reach SPR will be excluded from the mITT set. This analysis set will serve as the primary analysis set for efficacy and safety inference.

Full Treatment (FT) set is a subset of the mITT analysis set and will consist of all subjects who were vaccinated 3 times with Sci-B-Vac™ and had at least one visit following the 3rd vaccination.

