2.8 Final Analyses

The final analysis will include all the subjects who completed 12 months of follow-up, fully comply with the study protocol and have no inclusion/exclusion criteria violation. Subjects who early terminated the study but achieved the primary endpoint prior to withdrawal will be included as well (mITT population). If 95% of the subjects will be found seroprotected (having anti-HBs antibody concentrations $\geq 10\text{mIU/ml}$) then the primary endpoint will be achieved.

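### The early-termination success rule is not limited to individual exits, so an early study closure would count mid-course titres as Month 7 successes, and in the SAP's mITT set the bias can only be upward

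*Protocol*

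**What the plan says.** **Endpoint rule.** Protocol v2.0 sections 3.1 and 10.7.1 and SAP 2.5 and 4.4 define the primary endpoint as the proportion with anti-HBs of at least 10 mIU/ml at Month 7, one month after the third dose. They add: "Subjects early terminated from the study for any reason at any time while having an anti-HBs antibody concentrations" at or above 10 mIU/ml count as having met the endpoint.

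**Ways a subject can be terminated early.** Section 5.6 lists reasons for ending a subject's participation, among them "Request of regulatory agency, or Sponsor or Principal Investigator". Section 5.8 adds "The Sponsor reserves the right to discontinue the study at any time for any reason". Section 5.9 treats a subject as complete only after all Month 12 assessments.

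**Interim.** Section 10.1: "One interim analysis is planned for possible early termination of the study". The timing in section 10 is "at the time when approximately 50% of the subjects will reach Month 7 or early terminated the study". Protocol v2.0 gives no stopping boundary.

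**Who is analysed.** The protocol v2.0 mITT set (10.4.1) needs one dose and one follow-up visit, so subjects below 10 mIU/ml stay in it. SAP 2.4 differs: "Subjects who did not complete the full-course of vaccination (i.e. 3 injections) and did not reach SPR will be excluded from the mITT set". SAP 2.8 describes the final analysis as 12-month completers, with this addition: "Subjects who early terminated the study but achieved the primary endpoint prior to withdrawal will be included as well".

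Neither document says how ongoing subjects are to be analysed if the study is closed.

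**The concern.** Closing the study ends participation for everyone still in it, at the sponsor's request, which falls within the wording of the rule. A subject with 10 mIU/ml or more after one or two doses would then be scored as a Month 7 success after three. Individual drop-out, planned at about 20%, is spread over time and arises subject by subject. A closure affects up to half the sample at once, through a decision that may follow sight of the data in an open-label, single-arm study.

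The direction of the bias depends on the analysis set. Under SAP 2.4 an ongoing subject who has not had dose 3 either adds a success or leaves the denominator, so the rate can only go up. Under the protocol v2.0 set the subject stays either way, and the rate is usually pulled down. At stake is whether the batch qualifies as a reference standard on a rate that does not describe the full course.

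**Working it through.** **Inputs from the documents**
- Success criterion: exact lower bound of at least 86.0% (95% minus a margin of 9.0 points; protocol 10.3 and 10.7.1, SAP 4.4).
- Level: "The overall significance level for this study will be 5% using two-tailed tests", so the two-sided 95% interval is used.
- Recruited 84, evaluable 70 (protocol 10.3); interim at about 50%, so about 42 of 84.

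**Assumptions**
- At closure 42 subjects have a Month 7 titre, and 42 are ongoing with none yet given dose 3.
- Seroprotection among the ongoing subjects is not in the documents, so a range is shown.

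**Formula.** Clopper-Pearson lower bound for x successes in n: the 0.025 quantile of Beta(x, n − x + 1).

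**Step 1: the plan's own figure.** For n = 70, 66/70 (94.3%) gives 86.01%, which reproduces the stated 86.0%; 65/70 gives 84.1%. The rule is therefore at least 66/70. The pass probability is 2.5% at true SPR 86% and 72.8% at true SPR 95%. The sample-size text mentions a one-sided 95% interval; that also needs 66/70 (65/70 gives 85.6%).

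**Step 2: Month 7 results only.** For n = 42, 41/42 gives 87.4% and 40/42 gives 83.8%, so 41 are needed. P(X ≥ 41 | 42, 0.86) = 1.4%; at 0.95 it is 37.2%.

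**Step 3: SAP 2.4 set.** With k ongoing subjects protected and the other 42 − k removed, n = 42 + k and the k count as successes. The rate becomes (x + k)/(42 + k), which is never below x/42.

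| Ongoing protected, k | n | Successes needed | Needed among the 42 at Month 7 | Pass probability at true SPR 86% |
|---|---|---|---|---|
| 13 | 55 | 53 | 40 | 5.4% |
| 29 | 71 | 67 | 38 | 28.2% |
| 38 | 80 | 75 | 37 | 45.4% |

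With k = 29, the Month 7 requirement falls from 41/42 (97.6%) to 38/42 (90.5%). The expected rate rises from 86% to (0.86 × 42 + 29)/71 = 91.7%.

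If k is random with mid-course seroprotection of 50% to 95%, the pass probability is 13% to 44%. With 92 enrolled, as in SAP 2.4, and a 46/46 split, it is 15% to 46%, against 0.8% on the 46 Month 7 results.

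**Step 4: protocol v2.0 mITT set.** All 84 stay, and 79 successes are needed. This step scores ongoing subjects below 10 mIU/ml as failures, which the protocol does not state. With k = 29 the most that can be reached is 42 + 29 = 71, so no batch passes. With mid-course seroprotection of 50% to 95%, the expected SPR is 68.0% to 90.5% at true SPR 86%, and 72.5% to 95.0% at true SPR 95%. It is pulled down unless mid-course protection is at least as high as the true Month 7 rate.

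**The case against.** **Closure is only a possibility.** Protocol 10.1 says so, and the later SAP plans to continue: SAP 2.7 has the first interim reported, a second after all third injections, and SAP 2.8 an analysis after 12 months. This stands and lowers the urgency. It withdraws neither the right in 5.8 nor the purpose given in 10.1.

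**Withdrawal and study termination have separate sections, and SAP 2.8 and 4.4 speak of withdrawal.** This suggests that individual exits were in mind. The endpoint rule does not say so, and 5.6 includes sponsor request.

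**A result close to Month 7 is already planned.** The FT set needs three vaccinations and a later visit, and the primary endpoint is described on it too. At the first interim, SAP Table 14.2-2 shows mITT subjects who completed Month 7. A reader might infer that the SPR becomes meaningless after closure; these displays, and the real Month 7 results of about half the sample, show that it does not. But they are supportive and do not correct the primary analysis.

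**SAP 2.8 might be read as a certain pass.** Taken alone, it would drop Month 7 failures who had not reached Month 12. With 36/42 at Month 7 and 29 ongoing successes, that leaves 65/65 (lower bound 94.5%). The documents do not support this as the intended analysis. SAP 2.8 calls its population mITT, 2.4 removes non-responders only if they lack three injections, and 4.4 has no 12-month condition.

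**Opposite conclusions from the same data might be inferred.** At the expected counts for true SPR 86% this does not happen: 36/42 (lower bound 71.5%), 65/71 (82.5%) and 65/84 (66.9%) all fail. The two mITT definitions can disagree at other counts, such as 69/71 (90.2%) against 69/84 (72.3%), but that depends on scoring ongoing subjects below 10 mIU/ml as failures.

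**The inputs are assumed.** This stands. A later closure affects fewer subjects, and subjects below 10 mIU/ml who have had dose 3 would stay in the SAP denominator.

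**Conclusion.** The concern holds as a conditional one. If the study is closed early, the rule as written admits titres taken before dose 3 as Month 7 successes, and combined with the SAP 2.4 exclusion it biases the primary SPR upward only. For a closure at the halfway point and a true SPR of 86%, the chance of wrongly passing is about 28% (5% to 45%). That is roughly 11 times the 2.5% of the 70-subject design and 20 times the 1.4% from Month 7 results alone.

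These sizes rest on the 42/42 split, on no ongoing subject having had dose 3, and on 13 to 38 ongoing subjects being protected. Under the protocol v2.0 set the error usually runs the other way. The documents do not show that closure is planned, or that every ongoing titre becomes a Month 7 result: only those at 10 mIU/ml or more become successes.

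**What to change.** State in protocol 3.1 and 10.7.1 and in SAP 2.4, 2.5, 2.8 and 4.4 that the early-termination rule does not apply when the study is closed by the sponsor or an authority. The primary SPR then uses every subject with a Month 7 titre, success or failure, whether or not Month 12 was reached. Subjects who have not reached Month 7 are not evaluable for the primary endpoint and are reported separately.

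At the same time, align the mITT definitions in protocol 10.4.1 and SAP 2.4, and bring the wording of SAP 2.8 into line with 2.4 so that it cannot be read as removing Month 7 failures.

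The text change is small, but the loss of evaluable subjects is not. After a closure at 42 Month 7 results, success needs 41/42, and a batch with a true SPR of 95% passes only about 37% of the time, against about 73% with 70 evaluable subjects. That is what stopping at about half the planned recruitment costs, and the sponsor should weigh it before closing the study on the interim.
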